Hypothesis 1a: A 12-week BA-R intervention in ARF survivors will be feasible, as demonstrated by an average accrual rate of 1.5 patients per month, completion of $\geq 80\%$ of the 12-week phone calls, and $\leq 15\%$ of enrolled patients lost to follow-up at the end of the 12-week intervention.

Hypothesis 1b: At the end of the 12-week BA-R intervention, ARF survivors in the BA-R versus “usual care” group will demonstrate decreased depressive symptoms, less impairments in physical function and quality of life, and reduced healthcare utilization

Hypothesis 1c: We will conduct qualitative research, using thematic analysis, to identify key barriers and facilitators to engaging with the BA-R intervention, as well as perceived satisfaction, acceptability and feasibility of BA-R.

Aim 2: To evaluate the association between resilience, coping and social engagement with depressive symptoms and the association between these factors and the BA-R intervention among at-risk ARF survivors from Aim 1.

Hypothesis 2a: Increased resilience, adaptive coping, and social engagement are associated with fewer depressive symptoms using the combined patient cohort from the BA-R and control groups in Aim 1

Hypothesis 2b: At the end of the 12-week intervention, ARF survivors in the BA-R versus “usual care” control group will demonstrate improvements in coping, resilience and social engagement.

Hypothesis 2c: We will conduct qualitative research, using thematic analysis, to identify the role of resilience, coping, and social engagement in recovery from ARF.

Aim 3: To evaluate measurement properties (e.g., sensitivity, specificity, positive/negative predictive values) of two commonly-used depression screening instruments (i.e., Hospital Anxiety and Depression Scale (HADS) and Personal Health Questionnaire Depression Scale-8 (PHQ-8)) for detecting depressive symptom severity using a “gold standard” depression measure (i.e., Structured Clinical Interview for the Diagnostic and Statistical Manual of Mental Disorders 5th Edition (SCID-5)), in at-risk ARF survivors from Aim 1.

Hypothesis 3: The HADS and PHQ-8 will adequately discriminate depressive symptom severity compared to the SCID-5 “gold standard” using the combined patient cohort from the BA-R and control groups in Aim 1.

3. Background (briefly describe pre-clinical and clinical data, current experience with procedures, drug or device, and any other relevant information to justify the research)

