Personal Health Questionnaire (PHQ-8)⁴⁶: The PHQ-8 uses a 4-point Likert scale to assess depressive symptoms (Scores 5-9 indicate “mild” symptoms, 10-14 “moderate”, and ≥ 20 “severe” depressive symptoms). While PHQ-9 has been validated for diagnostic accuracy in many other populations, it has not been evaluated against a “gold standard” clinician diagnostic interview in ARF survivors. As commonly done for medicolegal reasons in research, the PHQ-8, rather than PHQ-9, is used since it removes a question regarding suicidal ideation.⁴⁸

Structured Clinical Interview for the DSM-5 (SCID-5) – Mood Disorders Section¹⁰⁹: is a semi-structured, clinician-based psychiatric interview for making diagnoses according to Diagnostic and Statistical Manual of Mental Disorders-5 (DSM-5).¹¹⁰ Prior versions are validated^{143,144} and demonstrate high inter-rater reliability for the diagnosis of major depression.¹¹¹⁻¹¹⁴

Activity Measure for Post-Acute Care Computer Adaptive Test (AMPAC-CAT): will be licensed for this study to evaluate the functional status of participants. The AMPAC has 269 items across three domains (basic mobility, daily activity and applied cognitive). The computer adaptive test, validated for use in the currently proposed post-acute care settings, requires a mean of 22 items from the item bank (administration time: 6 min.).^{87,88,115,116} The test will be administered, using a computer, by blinded research staff.¹¹⁷

Health-Related Quality of Life (HR-QOL): will be measured using the EQ-5D-5L.

Healthcare Utilization: We will collect data on the post-discharge healthcare utilizations, including in-patient admissions to hospitals, and skilled nursing, acute and sub-acute rehabilitation facilities (Table 4). Moreover, we will collect data on utilization of out-patient mental health and physical rehabilitation services (Table 1). We will evaluate these measures using existing methodology from our prior research in ARF survivors.¹¹⁸⁻¹²¹

Table 4. Secondary outcomes

Description	Instrument (# items; time to complete (minutes))	Baseline	Week 6	End of Intervention
Depressive Symptoms	HADS (7 items; 2min) PHQ-8 (8 items, 2min) SCID-5 ^a (30 min)	x	x	x x x
Functional status	AMPAC-CAT(~22 item; 6 min) Return to baseline work/activity (8 items; 3 min)	x		x x
Health-Related Quality of Life	EQ-5D-5L (2 min)			x
Employment status				x

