Health Care Utilization and Estimated Costs	Admission to hospital, nursing & rehabilitation facilities; plus mental health & physical rehab utilization (8 min)			x
Survival status	Patient/Proxy (<1 min)			x
Coping Style	Brief Cope (28 items; 10 min)	x		x
Social Engagement	BADS (25 items; 5 min)	x		x
Resilience	CD RISC (25 items; 10 min)	x		x
Cognitive Function	MoCA-BLIND (8 questions; 5 min)			x
PTSD	IES-R (22 items; 6 min)			x

Abbreviations: HADS= Hospital Anxiety and Depression Scale, SCID-5= Structured Clinical Interview for DSM-5 (Mood Disorders Section only), AMPAC-CAT= Activity Measure for Post-Acute Care--Computer Adaptive Test, BADS= Behavioral Activation for Depression Scale, CD RISC= Connor-Davidson Resilience Scale

a: semi-structured interview

Brief Cope: Coping strategies will be assessed using the self-reported 28-item Brief Cope Scale.⁹⁴ The scale is a valid and reliable, used in medical populations, with strong measurement properties.^{94,120,122} It will assess active (e.g. problem solving) versus avoidant coping (e.g., behavioral disengagement, self-blame).

Behavioral Activation for Depression (BAD) Scale: This 25-point scale⁹⁵ assesses social engagement and other aspects of behavioral activation. We demonstrated BADS's validity in medical populations with depressive symptoms and its sensitivity to change with depression treatment.¹⁶

Connor-Davidson Resilience Scale (CD RISC): This 25-item scale⁹⁶ assesses resilience. It has been validated in a variety of patient populations and specifically used in research involving ARF survivors.^{102,105,106}

Adherence to the BA-R Intervention: will be evaluated as done in prior studies^{83,85} by: (1) measuring the number of phone attempts needed by the OT to reach the participant for each session, and (2) calculating the proportion of sessions fully completed (with sub-analysis for number partially completed).

Montreal Cognitive Assessment (MoCA) – BLIND: is a validated phone-based version of the original MoCA,¹²³ a rapid screening instrument for mild cognitive dysfunction. The MoCA - BLIND assesses different cognitive domains including attention and concentration, memory, language, conceptual thinking, calculation and orientation. It will take 5 minutes to administer the MoCA-BLIND.

Impact of Events Scale – Revised (IES-R): This is the most commonly used instrument for assessing PTSD symptoms in ARF survivors.¹⁰⁷ It has 22 items, is reliable and valid.¹²⁴

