Hypothesis 1b: *At the end of the 12-week BA-R intervention, ARF survivors in the BA-R versus “usual care” group will demonstrate decreased depressive symptoms, less impairments in physical function and quality of life, and reduced healthcare utilization.* Analyses will follow a modified intention-to-treat principle and a 2-tailed p<0.05 is statistically significant. Patient mortality is expected to occur infrequently (see Sample Size above) and not to differ by treatment vs. control group; therefore, all analyses will be conducted for 12-week survivors only. The analysis will include separate comparisons of the effect of the BA-R intervention vs usual care control on each of the blinded outcomes in Table 4. These analyses will estimate the average treatment effect, i.e. the difference in the mean 12-week outcome comparing the BA-R intervention to the usual care control, using the precise locally efficient augmented simple estimator (PLEASE) described in Colantuoni and Rosenblum[REF: 135]. This method for estimating the average

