treatment effect is similar to the analysis of covariance (ANCOVA) approach in that it incorporates the baseline outcome (if measured) which, if correlated with the 12-week outcome, can improve the precision of the estimated average treatment effect [Ref 134]. This method also accounts for more general patient drop-out models than the ANCOVA approach. Specifically, the ANCOVA approach is valid under completely at random drop-out, whereas the PLEASE is valid under missing at random drop-out, i.e. when patient drop-out differs by treatment group or across levels of the baseline outcome or other measured variables at baseline. The PLEASE requires a priori specification of three models: an outcome regression model (fit separately for each treatment group) that will include age, gender and the baseline outcome (if measured), a propensity score model that will include age, gender and the baseline outcome (if measured) and a drop-out model (fit separately for each treatment group) that will include age, gender, and the outcomes measured at baseline (HADS, Brief Cope, CD RISC, BADS). As exploratory analyses, the 12-week outcomes (e.g. HADS scores) will be summarized (summary statistics including counts of missing values and histograms) and the correlation of the baseline (if appropriate) and 12-week outcomes will be computed, separately by treatment arm. Patient mortality, drop-out and missing data will be described for all variables, separately for treatment vs control groups. Patient characteristics will be compared between those with vs. without missing outcomes (due to drop-out and missing values).¹³⁶⁻¹³⁸

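### For EQ-5D-5L, IES-R and (as inferred) PHQ-8, the outcome and propensity models adjust for age and gender only, although baseline HADS is collected and could be used

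*Combined protocol and SAP*

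**What the plan says.** Under Hypothesis 1b, Section 7c applies PLEASE separately to "each of the blinded outcomes in Table 4" and requires three models to be fixed in advance:

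- Outcome regression: "an outcome regression model (fit separately for each treatment group) that will include age, gender and the baseline outcome (if measured").
- Propensity score: "a propensity score model that will include age, gender and the baseline outcome (if measured").
- Drop-out: a model "that will include age, gender, and the outcomes measured at baseline (HADS, Brief Cope, CD RISC, BADS"), with no exception by outcome.

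In Table 4 (Section 7b), the row "IES-R (22 items; 6 min") and the EQ-5D-5L row each carry a single mark, under end of intervention. The depressive-symptom row covers three instruments, "HADS (7 items; 2min) PHQ-8 (8 items, 2min) SCID-5", with one baseline mark, one week-6 mark and three end-of-intervention marks. Table 1 (Section 4a) lists HADS in its block of measures taken at home before the intervention starts. It lists none of PHQ-8, EQ-5D-5L or IES-R. Hypothesis 1b names "less impairments in physical function and quality of life" among the expected benefits, so EQ-5D-5L serves a stated efficacy hypothesis.

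**The concern.** Section 7c itself justifies the method by the precision to be gained from a baseline value correlated with the 12-week outcome. The rule as written gives up that gain wherever the same instrument was not used at baseline, even when a closely related one was. HADS and PHQ-8 both measure depressive symptoms, yet the HADS comparison is adjusted for baseline depression and the PHQ-8 comparison is not. Randomisation is stratified by history of depression, not by current severity, so with 27 per arm some chance imbalance in baseline HADS is to be expected. The HADS result would be corrected for it, and the PHQ-8, IES-R and quality-of-life results would not. The further exploration of prognostic baseline variables in Section 7c is a secondary analysis meant to inform later trials, so it does not close the gap in this one.

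**Working it through.** **1. Covariates that each outcome receives (Section 7c with Tables 1 and 4)**

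| 12-week outcome | Own baseline? | Outcome and propensity models | Drop-out model |
|---|---|---|---|
| HADS | yes | age, gender, baseline HADS | age, gender, HADS, Brief Cope, CD RISC, BADS |
| EQ-5D-5L | no | age, gender | same |
| IES-R | no | age, gender | same |
| PHQ-8 | no (inferred) | age, gender | same |

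The PHQ-8 entry is an inference. In the text as read from the PDF, the Table 4 marks for the three depression instruments run together. One baseline mark for three instruments, with HADS alone named in Table 1 and in the Section 7c list, points to HADS. Other rows without a baseline, such as MoCA-BLIND, fall under the same rule. The point is confined to the three outcomes for which a depression score is a plausible predictor.

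**2. The plan's own precision figure.** The Sample Size paragraph gives 27 per arm, SD 4.2, two-sided 5% alpha, 80% power and a detectable HADS difference of 3.1 points. Recomputed:

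(1.960 + 0.842) × 4.2 × √(2/27) = 3.20 points (3.26 with the t distribution).

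The stated 3.1 is about 0.1 point optimistic, which does not affect this point. In SD units the detectable effect is 2.802 × √(2/27) = 0.76 SD. No power figure is given for EQ-5D-5L, PHQ-8 or IES-R, so 0.76 SD serves as the reference, with age and gender taken as non-prognostic.

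**3. Gain from one added baseline covariate.** Let ρ be the within-arm correlation of baseline HADS with the 12-week outcome. In large samples the variance is multiplied by 1 − ρ², and the detectable effect becomes 0.76 × √(1 − ρ²). Estimating an extra coefficient in each arm has a cost, so arm-specific regressions were also simulated: 27 per arm, standardised over all 54, no drop-out, 6,000 to 20,000 runs per value. The simulated ratio compares age, gender and one covariate with age and gender alone; ranges show the spread between repeated runs. The change in confidence-interval width is √ratio − 1.

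| ρ (assumed) | 1 − ρ² | Detectable effect, SD | Power at 0.76 SD | Simulated variance ratio | CI width |
|---|---|---|---|---|---|
| 0 | 1.00 | 0.76 | 80% | 1.02–1.03 | 1.0–1.5% wider |
| 0.2 | 0.96 | 0.75 | 82% | 0.98–0.99 | 0.5–1% narrower |
| 0.3 | 0.91 | 0.73 | 84% | 0.93–0.94 | 3–4% narrower |
| 0.4 | 0.84 | 0.70 | 86% | 0.86 | 7% narrower |
| 0.5 | 0.75 | 0.66 | 90% | 0.75–0.78 | 12–13% narrower |
| 0.6 | 0.64 | 0.61 | 94% | 0.64–0.66 | 19–20% narrower |

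The detectable-effect and power columns are large-sample values. The simulation covers the regression part of the estimator, not the full PLEASE procedure with its propensity and drop-out weights.

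**4. Chance imbalance.** One standard error of the difference in baseline HADS means is √(2/27) = 0.27 SD under unstratified allocation. At ρ = 0.5 it moves an effect not adjusted for HADS by 0.5 × 0.272 = 0.14 SD. That is half of the unadjusted effect's own standard error (0.136/0.272). Stratification by history of depression lowers this figure to the extent that history predicts baseline HADS, which the documents do not give.

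**The case against.** The strongest reply is that this is a choice about efficiency, not an error. The arms are randomised, so a model with age and gender adds no bias. A chance imbalance is already reflected in the width of the interval. A short covariate list fixed in advance is prudent when models are fitted separately in arms of 27, and Hypothesis 2a shows the same caution about overfitting. The outcomes are also peripheral. Feasibility is primary, HADS is the only efficacy outcome with a power statement and has its baseline, PHQ-8 mainly serves Aim 3, and PTSD is not named in Hypothesis 1b. All of this stands, and it limits the weight of the point. It does not defend the omission, because one added term gives the same model size already planned for HADS.

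A reader might infer more than the documents support:

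- *That these effects are adjusted for age and gender only throughout.* The drop-out model includes baseline HADS, Brief Cope, CD RISC and BADS for every outcome. With under 15% missing outcomes expected, it adds little precision, but it is part of the estimator.
- *That any disagreement between HADS and PHQ-8 would come from the adjustment alone.* Section 7b says HADS gives little emphasis to physical symptoms, so the two can differ in content.
- *That baseline AMPAC-CAT is a ready stand-in for quality of life.* Table 1 lists it outside the at-home block, Section 7c leaves it out of the outcomes measured at baseline, and it spans three domains. Adding three scores of which one is prognostic gave simulated variance ratios of 1.08 at ρ = 0, 1.04 at 0.2 and 0.98 at 0.3, so most of the benefit is lost.

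**Conclusion.** The point holds as a loss of precision in secondary outcomes. For EQ-5D-5L and IES-R, and for PHQ-8 if the reading of Table 4 is right, the two models that gain precision and correct imbalance contain age and gender only. Baseline HADS is collected but does not enter them. The size depends on a correlation that the documents do not give. The gain is negligible at 0.2, modest at 0.3 (about 7% of variance) and material from 0.4 upward (14% at 0.4, 22 to 25% at 0.5). The cost if HADS proves unrelated is about 2 to 3%. These figures assume 27 analysed per arm, no drop-out and non-prognostic age and gender. If age and gender do predict the outcome, ρ should be read as the correlation remaining after them. Nothing here implies bias or touches the feasibility conclusion. The change is worth making because it is cheap and loses little credibility only if it is made in advance.

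**What to change.** In Section 7c, Hypothesis 1b, amend the outcome-regression and propensity models so that the third covariate is the outcome's own baseline value or, for PHQ-8, IES-R and EQ-5D-5L, the baseline HADS depressive-symptom score. Fix this before any unblinded analysis. It takes one sentence, needs no new data, and keeps each model at three terms. State in the same place whether PHQ-8 is measured at baseline. If it is, its own value applies.

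Two tempting additions are best left out. AMPAC-CAT should not be offered as an alternative unless its baseline timing and a single score are confirmed, since an open choice defeats the requirement to specify the models in advance. Adding EQ-5D-5L to the baseline interview partway through enrolment would leave that covariate missing for everyone already enrolled, and the rule would then need imputation to work.

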A single cohort of patients will be used for all 3 Aims (i.e. both intervention and control groups recruited into the randomized controlled trial (RCT) will form a single cohort for analyses in Aims 2 and 3). We will enroll 54 patients from all Johns Hopkins Hospital adult ICUs. If patients are lost to follow-up, we will enroll up to 10 additional patients to obtain 12-week outcomes assessments on a total of 54 patients (27 in each group). Oral informed consent will be obtained from all participants.

Aim 1 Methods: We will conduct a single-site, pilot RCT (N=54) evaluating the feasibility (primary objective) and efficacy (secondary objective) of a 12-week behavioral activation-rehabilitation (BA-R) intervention versus “usual care”, in acute respiratory failure (ARF) survivors. We will evaluate the BA-R intervention via an RCT study design, with blinded outcome assessments. We will test the feasibility of this intervention (primary outcome) and its efficacy (secondary outcome) at the end of intervention. Figure 2 shows study timeline.

[figure not shown]
After return home, consented patients will be randomized to: (1) behavioral activation and rehabilitation (BA-R) intervention or usual care. Randomization will occur via web-based tool, using variable-sized

blocks from 2 to 4, and stratified by history of depression prior to ICU admission (based on chart review and patient interview). Baseline variables are detailed in Table 1 below.

Table 1: Baseline Variables

Variable	Collection	Measurement Scale
Patient Variables		
Age/sex/race	Chart review	Continuous/Binary/Categorical
Education (number of years/highest attainment)	Patient interview	Continuous/Categorical
Employment & Health Insurance status	Patient interview	Categorical
Comorbidity indices: Charlson (CCI) ^a & Functional (FCI) ^b	Chart review	Ordinal
Alcohol intake/misuse / Drug abuse	Chart review	Categorical
Physical function at baseline: AMPAC-CAT ^{87,88 c}	Patient interview	Continuous
ICU and Hospital Variables		
ICU admission diagnosis (e.g., sepsis, renal failure)	Chart review	Categorical
Severity of illness: APACHE II ^d	Chart review	Continuous
Benzodiazepine use and dosing ^{56,89,90}	Chart review	Continuous
Daily ICU Sedation Status: RASS ⁹¹	Chart review	Ordinal
Daily ICU Delirium Status: CAM-ICU ^{92,93}	Chart review	Categorical
Daily Minimum Glucose ⁹⁰	Chart review	Continuous
ICU and Hospital Length of Stay	Chart review	Continuous

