c. Statistical plan including sample size justification and interim data analysis.

Sample Size: As a pilot RCT, we aim to enroll a convenience sample of ~1.5 patients/month, for a total of 54 patients (based on 36 months of recruitment; see Timeline-Candidate Statement). Extensive experience enrolling ARF patients in prior studies by our group^{10,121,125-127} suggests this rate is feasible for a K-23 award at this study site. We expect an overall <15% missing completion rate due to mortality and loss to follow-up (in our prior study of >500 ARF survivors, loss to follow-up was 2% with 7% mortality at 6 months¹²⁵), thus, we expect 54 patients to complete the intervention. With 54 participants (27 in each group), assuming 5% alpha, 80% power and HAD SD of 4.2 points based on our prior research in ARF survivors^{89,90}, for our secondary aim of efficacy, we can detect a 3.1 point difference in HADS score between the 2 treatment groups, which approximates HAD's 2.9 point minimum important difference (MID) in ARF survivors.¹²⁸ This proposed enrollment rate and sample size is consistent with existing pilot/feasibility trials in ARF research.^{101,129,130}

Statistical Analysis

Hypothesis 1a: *A 12-week BA-R intervention in ARF survivors will be feasible, as demonstrated by an average accrual rate of 1.5 patients per month, completion of ≥80% of the intervention phone calls, and ≤15% of enrolled patients lost to follow-up for outcomes assessments at end of the 12-week intervention.* We will assess the total number of intervention phone calls completed per patient as a proportion of the number of intervention phone calls each patient is intended to complete (i.e., 9 intervention calls – weekly during first 6 weeks and bi-weekly for second 6 weeks of the 12-week protocol). We also will assess total number of intervention phone calls completed by all study participants as a proportion of total intervention phone calls expected in the study. We will calculate the number of patients completing the 12-month follow-up session as a proportion of the number of patients enrolled to measure loss to follow-up.

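### Does a six-covariate drop-out model, fitted by arm on about 0.5 to 5 expected drop-outs, need to be replaced?

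*Combined protocol and SAP*

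**What the plan says.** Section 7c (Statistical Analysis, Hypothesis 1b) estimates each 12-week treatment effect with PLEASE, which combines three models. One is "a drop-out model (fit separately for each treatment group) that will include age, gender, and the outcomes measured at baseline", listed as HADS, Brief Cope, CD RISC and BADS. With one score per instrument that makes six covariates. Section 7b describes Brief Cope as contrasting active with avoidant coping, so six is a minimum. The outcome regression is also fitted by arm, on age, gender and the baseline value where one exists. The stated advantage over ANCOVA is robustness to drop-out: "whereas the PLEASE is valid under missing at random drop-out".

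Deaths are outside this model, because "all analyses will be conducted for 12-week survivors only". Under Sample Size, section 7c says "We expect an overall <15% missing completion rate due to mortality and loss to follow-up" and cites an earlier study in which "loss to follow-up was 2% with 7% mortality at 6 months". Hypothesis 1a separately allows up to 15% for loss to follow-up alone. Section 4a adds that "we will enroll up to 10 additional patients to obtain 12-week outcomes assessments on a total of 54 patients".

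The plan names no link function, penalty, reduced model or rule for an arm with few or no drop-outs. ANCOVA appears as a comparator, not as a fallback.

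**The concern.** A binary model with more covariates than events is a familiar warning sign. With so few drop-outs, some combination of covariates will often separate drop-outs from completers perfectly or nearly so, and maximum likelihood then has no finite solution. The plan is alert to overfitting elsewhere: Hypothesis 2a allows at most four covariates in linear models on the whole sample of 54. The drop-out model has six, on half that sample, with a sparse binary outcome.

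At stake is the reason given for choosing PLEASE. If the drop-out model cannot be fitted, the protection against informative drop-out may vanish, or an occasional extreme weight may distort the estimate. The analyst would also have to choose a substitute with the data in hand, although the plan says the three models are to be fixed in advance.

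**Working it through.** **1. The plan's own figures.** Accrual: 1.5 per month × 36 months = 54, as stated ("for a total of 54 patients (based on 36 months of recruitment"). Replacement: 54 / (1 − 0.15) = 63.5, rounded up to 64 = 54 + 10, also as stated. Detectable difference, from "With 54 participants (27 in each group), assuming 5% alpha, 80% power and HAD SD of 4.2 points": 4.2 × √(2/27) × (1.960 + 0.842) = 3.20 points, or 3.26 with the t distribution, against the stated 3.1. This small discrepancy does not bear on the question; 3.1 serves only as a yardstick.

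**2. Expected drop-outs per arm** (arm size × loss rate).
- 2% loss: 27 × 0.02 = 0.54; 32 × 0.02 = 0.64.
- 15% loss: 27 × 0.15 = 4.05; 32 × 0.15 = 4.8.
- All ten replacements used: 10 / 2 = 5.

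Divided by six covariates, this is 0.09 (0.54 / 6) to 0.83 (5 / 6) events per covariate. Because lost patients are replaced, 27 per arm goes with almost no losses and 32 per arm with about ten. The coherent pairings are therefore 27 at about 2% and 32 at about 15%.

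**3. Arms with no drop-outs.** P(at least one such arm) = 1 − [1 − (1 − r)^n]².
- 2%: 0.82 (n = 27), 0.77 (n = 32).
- 8% (an assumed intermediate rate): 0.20, 0.13.
- 15%: 0.025, 0.011.

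In such an arm a weight of 1 for everyone is the correct answer.

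**4. How often there is no finite fit.** A linear-programming test for separation was applied to simulated arms with six covariates (assumed correlations 0 to 0.4, assumed logistic link). By number of drop-outs in an arm:

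| Drop-outs | Arms with no finite fit |
|---|---|
| 1 | 100% |
| 2 | 78–81% |
| 3 | 42–50% |
| 4 | 22–26% |
| 5 | 10–14% |

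A single drop-out always fails, because it has one gender. Failure in at least one arm occurs in over 99% of trials at 2% loss and 84–93% at 8%. At 15% it occurs in about 59–64% with 27 per arm and 37–46% with 32 per arm.

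**5. What a failed fit does.** Fitted completion probabilities for completers usually approach 1, so their weights do too. Over all simulated arms, every completer weight was about 1 in 92–96% at 2%, 49–65% at 8% and 18–32% at 15%. A weight above 20 occurred in 0.2–0.8% of arms.

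**6. Effect on the HADS estimate.** A reconstructed three-model weighted estimator (SD 4.2, assumed baseline to 12-week correlation 0.5) was compared with a version using one pooled drop-out model containing treatment and baseline HADS.

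| Loss | Median absolute difference | 95th percentile |
|---|---|---|
| 2% | 0.00 | 0.04–0.07 |
| 8% | 0.02–0.04 | 0.27–0.30 |
| 15% | 0.10–0.11 | 0.45–0.52 |

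The standard error of the contrast is 4.2 × √(2/27) = 1.14, or 1.14 × √(1 − 0.5²) = 0.99 after baseline adjustment. The median shift at 15% is thus about a tenth of a standard error, and the largest 95th percentile about half of one.

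**7. What the simpler model would buy.** In a further simulation (assumed covariate correlation 0.3) root mean squared error fell by at most 0.8% at 2–8% loss and by about 1–6% at 15%, partly through avoiding rare extreme weights. Results were nearly identical to using no drop-out weights. When drop-out depended on CD RISC differently in the two arms, bias grew from −0.10 to −0.19 points.

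The pooled model also needs rescue rules. Without them it has no finite fit in 78–84% of trials at 2% and 13–20% at 8%. A rule setting weights to 1 below five drop-outs in total would apply in over 99% of trials at 2% and 40–59% at 8%, which is largely what separation already produces.

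**The case for a change.** The strongest case for a change is about prespecification rather than bias. The plan says all three models are set beforehand, yet one of them often cannot be fitted as written. The analyst must then improvise after seeing who dropped out, and a reader could not tell whether the claimed missing-at-random protection was in force. Brief Cope, CD RISC and BADS enter the HADS analysis only through this model, so a failed fit loses them. The pilot is also meant to inform a larger trial, and a fallback rule costs only a sentence or two.

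The event count and the absent fallback stand. The consequence does not follow at the same strength. The obvious remedies (a penalised fit, a reduced or pooled model, weights of 1) would be familiar to any analyst. Where the two ends of that range were compared, the answers nearly coincided, so there is little room for a favourable choice. Half a standard error in the upper tail at 15% loss could move a borderline p-value, but only for a secondary outcome at the plan's ceiling. Nor would the problem be hidden: Hypothesis 1b already promises a description of drop-out and missing data by arm, and a comparison of patients with and without outcomes. Finally, cutting the covariates gives up in every trial the predictors that a failed fit gives up only in some.

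**Conclusion.** No change to the plan is needed. The drop-out model is over-specified for the drop-outs expected, and as an ordinary logistic fit it would often have no finite solution. At low loss the usual result, weights near 1, is right or nearly so. At the 15% ceiling the median effect on the HADS contrast is about 0.1 points against a stated 3.1. The outcome regression continues to adjust for age, gender and the baseline value where measured. The primary feasibility outcome does not use this model.

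What remains is an unwritten computing convention that the trial statistician can settle when fitting the model, and a genuine trade-off between a richer drop-out model that may not fit and a sparser one with a weaker missing-at-random argument.

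This rests on assumptions: a logistic link, which the documents do not state; simulated covariate distributions and correlations; and a reconstruction of the estimator, whose defining paper is not part of the documents. Only HADS was simulated. For the Hypothesis 2b outcomes, and for outcomes with no baseline value such as EQ-5D-5L, a small effect is a reasonable expectation, not a computed one. The event counts are plain arithmetic and are firm.
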